# 3.6.2 Off-Study Criteria

Patient requests to be withdrawn from study

Version Date: 01/01/2024

- Death
- Physician's determination that withdrawal is in the patient's best interest.
- Patients who receive non-protocol therapy for progression to symptomatic myeloma may remain on study for evaluation (by phone, email, or clinic visit) of survival per study schedule at the discretion of the investigator.
- Patients who have not progressed but choose to continue lenalidomide maintenance beyond 32 cycles at an outside facility may stay on study at the discretion of the investigator.
- Permanent loss of capacity to give consent
- Screen failure
- Lost to follow up

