# 1.1.2 Secondary Objectives

- To determine biochemical and symptomatic progression free survival (PFS)
- To determine duration of response (DOR)
- To determine duration of minimal residual disease (MRD) negative complete response (CR), and to estimate the rate of durable MRD(-) CRs (greater than one year)
- To evaluate toxicity of combination therapy (carfilzomib, lenalidomide, and dexamethasone)
- To evaluate biological activity of carfilzomib and correlate to clinical outcomes (gene expression profiling on pre- and post-carfilzomib exposure bone marrow samples) NOTE: This endpoint no longer applies as of Amendment H (version date 06/12/2017).
- To determine overall survival (OS)
- To compare the MRD (-) CR rates between patients enrolled from 2012-2014 vs. enrolled in 2017 and later years

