# 3.1.2 Maintenance and Ongoing Treatment or Follow-Up

After 8 cycles, patients will proceed to extended dosing phase I of lenalidomide (Days 1-21 of 28 day cycle) for 12 cycles. After 12 cycles of extended dosing of lenalidomide, patients who maintain their current clinical response and do not meet criteria of PD as defined in Section 6.3 will have the option to continue lenalidomide as clinically indicated for an additional year on extended dosing phase II.

After 2 years of maintenance, patients will be followed by clinical and laboratory examination every 3-6 months until disease progression requiring treatment. If patients progress, they may be contacted by phone or email to gather survival information. (Note: patients who have not progressed after 2 years of maintenance therapy, but decide to continue lenalidomide maintenance at an outside facility, may also be followed on this protocol as above for long term follow-up at the discretion of the investigator. This follow up will consist of clinic and laboratory examination, however, if the patient is undergoing these investigations at an outside facility, follow-up can be limited to NIH investigator-patient or NIH investigator-outside physician communication of test results.)

[figure not shown]
Of note: On October 19, 2015, the study was closed to accrual for administrative reasons. Eighteen patients had enrolled at that time. Effective with Amendment H (version date 06/12/17), the study status will change to "Open-Recruiting" to allow for enrollment of the remaining 10-12 patients as per the statistical analysis plan of this protocol.

Version Date: 01/01/2024

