- g. Baseline bone marrow aspiration and biopsy will be sent to Dept. of Pathology, flow cytometry, FISH/cytogenetics, CD 138 sorting/GEP/storage ([name] Lab) and heavy/light chain immunoglobulin rearrangement (optional) and/or NRAS/KRAS mutations in Molecular Pathology (optional). For screening eligibility purposes, an outside bone marrow may be used in which case a baseline at the NIH will also be performed. **Note:** As of February 6, 2023, all participants have completed the maintainance phase (C32) thus bone marrow and peripheral blood research samples will be sent to [name]'s lab on a case to case basis.
- h. FOOTNOTE NO LONGER APPLIES/DELETED IN AMENDMENT M (version date 07/20/2018). PREVIOUS TEXT: Optional Cycle 1 Day 2 bone marrow aspirate alone sent for CD138 sorting (GEP studies and microenvironment studies). NOTE: This no longer in effect with Amendment H (version date 06/30/2017).
- i. Bone marrow aspirate and biopsy can be performed +/- 21 days of intended cycle day. Bone marrow aspirate and biopsy will be sent to Hematology Section, Department of Lab Medicine (DLM), flow cytometry (bone marrow immunophenotyping of plasma cells), CD 138 sorting/GEP/storage, and +/- heavy/light chain immunoglobulin rearrangement and/or NRAS/KRAS mutations in Molecular Pathology (optional). In follow up period, PET/CTs will be done approximately annually.
- j. At minimum, follow-up will be every 3-6 months until progression of disease, or death. Patients may be followed at more frequent time intervals if clinically indicated, i.e. following post-therapy toxicity. Patients who have progressive disease while on study will be followed with restaging scans and laboratory tests as clinically indicated. Patients who are taken off treatment will continue to be followed for survival by phone or clinic visit. Patients who finish all 32 cycles of treatment will be followed at least every 6 months by clinic visit with laboratory evaluation and by bone marrow biopsy yearly at the discretion of the investigator. Of note, patients who do not progress, but decide to

*Version Date:* 01/01/2024

continue or resume therapy at an outside facility, may be followed by clinical and laboratory examination every 3-6 months. Alternatively, this data may be captured by investigator-patient or investigator-physician phone or email communication if the required examinations have been performed at the outside facility.

- k. At disease progression, marrow and FDG-PET/CT are optional.

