## 6.1.1 Long-term follow-up data collection

When patients enter the long-term follow-up period, the following data will be collected:

- adverse events related to Carfilzomib
- survival status which will be collected by phone or clinic visit
- additional cancer therapy received

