## 10.2 STATISTICAL ANALYSIS OF SECONDARY/EXPLORATORY ENDPOINTS

Secondary endpoints are duration of response and progression free survival (both biochemical progression and progression to overt symptomatic multiple myeloma). Duration of response is defined as time from response to disease progression or death. Progression free survival is defined as time of study entry to progression or death. Duration of response and progression free

*Version Date:* 01/01/2024

survival will be estimated using the Kaplan-Meier and log-rank methods. Secondary endpoints will also include rate and duration of MRD-negative CR and OS.

A number of correlative studies will be performed in order to assess carfilzomib in vitro biological activity and investigate minimal residual disease in SMM. Minimal residual disease will be further explored using multi-parametric flow cytometry, PCR-based techniques, and advanced imaging.

Beginning with Amendment L (version date 05/17/2018), the secondary objectives will also include:

- 1. To estimate the durable MRD (-) CR rate, estimating the fraction of patients who have an MRD (-) CR for 1 year as a minimum. This fraction will be estimated along with a 95% two-sided confidence interval.
- 2. To compare the outcomes among the 18 patients enrolled in 2014 or earlier to the 32 enrolled in 2017 or later because the diagnostic criteria for SMM vs. MM were revised in 2014 after the 18th patient was enrolled. The MRD (-) CR rates will be compared between these two cohorts of patients using a two-tailed Fisher's exact test. All other comparisons of outcomes between the two cohorts will be interpreted as exploratory and will be done using appropriate non-parametric statistical tests without adjustment for multiple comparisons.
- 3. To obtain and report safety data on all enrolled evaluable patients to fully characterize the safety of the regimen in a modestly large number of subjects treated on one protocol.

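### The protocol makes survival follow-up after progression optional in two places and required in two others, so the secondary overall survival estimate can be biased upward

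*Combined protocol and SAP*

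**What the plan says.** Section 1.1.2 lists OS among the secondary objectives, and section 10.2 repeats it: "Secondary endpoints will also include rate and duration of MRD-negative CR and OS". Section 10.2 gives OS no time origin, censoring rule or sensitivity analysis.

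Four places bear on survival follow-up once disease progresses:

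- Section 3.1.2: "If patients progress, they may be contacted by phone or email to gather survival information".
- Section 3.6.2, in the list of off-study criteria, on those whose disease has become symptomatic and who start treatment outside the protocol: "may remain on study for evaluation (by phone, email, or clinic visit) of survival per study schedule at the discretion of the investigator".
- Section 3.4, footnote j: "Patients who are taken off treatment will continue to be followed for survival by phone or clinic visit". The same footnote sets the regular visit schedule: "At minimum, follow-up will be every 3-6 months until progression of disease, or death".
- Section 6.1.1, among the data to be collected when patients enter long-term follow-up: "survival status which will be collected by phone or clinic visit".

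Section 3.6.1 lists progression as a reason for removal from protocol therapy.

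**The concern.** A site that takes a patient off study under 3.6.2 stops learning whether that patient is alive, and it does so just after symptomatic progression, when the risk of death has probably risen. In an OS analysis that patient is censored near progression. Standard estimators assume that those censored have the same outlook as those still followed. Here they would have a worse one, and because staying on study is discretionary, the choice could itself depend on prognosis. Deaths would be missed selectively and OS would read too high. With 50 evaluable patients planned, a few such losses can move the curve. Section 12.3 names possible prolongation of overall survival among the potential benefits of early treatment, so the estimate is likely to be read with interest even though it is secondary.

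**Working it through.** **Reading the rules together**

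| Place | Who is covered | Force | Who decides |
|---|---|---|---|
| 3.1.2 | patients who progress | optional | not named |
| 3.6.2 | those on non-protocol therapy for symptomatic myeloma | optional | investigator |
| 3.4, footnote j | patients taken off treatment | required | – |
| 6.1.1 | patients who enter long-term follow-up | required | – |

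Because progression is a reason to leave therapy (3.6.1), a patient who progresses on treatment is taken off treatment and falls under footnote j. If that patient then starts other therapy for symptomatic myeloma, 3.6.2 applies as well. One rule requires survival follow-up and the other leaves it to the investigator. No text ranks the two.

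**Size of the possible bias**

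The documents state no OS rate, event count or power, so there is no figure to reproduce. Every rate below is an assumption.

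Inputs: 30% progress by 5 years; death hazard 0.01 per year without progression and h1 = 0.12 per year after it; a fraction f of *all* progressors is censored at progression. Since 3.6.2 covers only treated symptomatic progressors, applying f to all of them makes this an upper illustration.

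- Progression hazard: λ = −ln(1 − 0.30)/5 = 0.0713 per year. Let a = λ + 0.01 = 0.0813.
- Alive without progression: P0(t) = exp(−a·t).
- Alive after progression: P1(t) = [λ/(a − h1)] × [exp(−h1·t) − exp(−a·t)].
- True OS = P0 + P1. At 5 years: 0.6659 + 0.2159 = 0.8818. At 8 years: 0.5217 + 0.2561 = 0.7778.
- With a fraction f censored, Kaplan-Meier tends in large samples to exp(−∫h(u)du) from 0 to t, where h = [0.01·P0 + 0.12·(1 − f)·P1] / [P0 + (1 − f)·P1].
- Check at f = 1: h = 0.01, giving exp(−0.05) = 0.9512 and exp(−0.08) = 0.9231.

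| Progressors lost | 5-year estimate | Excess (points) | 8-year estimate | Excess (points) |
|---|---|---|---|---|
| 0% | 88.18% | 0 | 77.78% | 0 |
| 25% | 89.64% | 1.5 | 80.52% | 2.7 |
| 50% | 91.25% | 3.1 | 83.74% | 6.0 |
| 100% | 95.12% | 6.9 | 92.31% | 14.5 |

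Range, with half of progressors lost:

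- Post-progression death hazard of 0.08 to 0.20 per year, other inputs unchanged: excess 2.1 to 4.7 points at 5 years and 4.2 to 8.6 at 8 years.
- Five-year progression of 10% to 50% and post-progression hazard of 0.10 to 0.20: excess 0.9 to 7.2 points at 5 years and 2.0 to 11.4 at 8 years.

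The bias is upward in every case.

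For scale, with 50 patients and no other censoring, the 95% half-width is 1.96 × √(0.8818 × 0.1182/50) = 8.9 points at 5 years and 1.96 × √(0.7778 × 0.2222/50) = 11.5 points at 8 years.

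**The case against.** The best defence is that the plan already intends survival follow-up and only the wording is loose. The bullet in 3.6.2 can be read as a permission: starting other therapy need not end participation. Progression alone is not an off-study criterion. The word *may* in 3.1.2 can be read as allowing phone or email in place of a visit. Footnote j is as much protocol text as 3.6.2. These readings are possible, but none is stated, and a site that ends follow-up under the discretionary clause would still comply with 3.6.2.

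Several stronger readings are tempting and are not supported:

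- A reader might infer that both optional passages hand the decision to the investigator. Only 3.6.2 does. The discretion clause in 3.1.2 concerns patients who have *not* progressed and continue lenalidomide elsewhere.
- A reader might infer that 3.6.2 overrides footnote j. The documents set no order of precedence.
- A reader might take 3.6.2 to cover every progressor. Biochemical progressors not treated for symptomatic myeloma are outside that bullet.
- A reader might take 6.1.1 to bind for every progressor. It applies on entry to long-term follow-up, and the protocol does not say that all progressors enter it.
- A reader might infer that patients have already been lost this way. Nothing in the documents shows it.

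Two points on size also stand. The 8-year figures flatter the concern: section 10.2 places 32 of the 50 planned patients in 2017 or later, so at the version date of 01/01/2024 they had at most about 7 years of follow-up, and the 5-year bias is about half as large. OS also has no powered test or decision rule, and "survival will be estimated using the Kaplan-Meier and log-rank methods" is written for duration of response and progression-free survival. Its use for OS is an inference, though any estimator that treats these patients as non-informatively censored has the same weakness.

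**Conclusion.** The conflict is in the current text and should be resolved. As written, survival follow-up may lawfully stop after symptomatic progression in some patients, and OS can then be overstated. The direction is secure provided the risk of death rises after progression. The amount is not known. On the assumed rates it is about 1.5 to 6.9 points at 5 years for 25% to 100% of progressors lost, and less if only treated symptomatic progressors are affected. Losing half gives 3.1 points at 5 years, about a third of the 8.9-point sampling half-width. More patients do not remove this error, and it works in one direction. It concerns one secondary endpoint. The MRD-negative CR estimate does not depend on it.

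**What to change.** Reconcile the passages to the rule already in footnote j:

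- Section 3.1.2, sentence on patients who progress: change *may be contacted* to *will be contacted*. Leave the separate note on patients who have not progressed as it is.
- Section 3.6.2, bullet on non-protocol therapy only: replace the discretionary wording with *will remain on study for survival follow-up*. Leave the other off-study criteria unchanged, including patient request, the physician's best-interest determination, loss of capacity to consent and loss to follow-up.
- For any progressor already taken off study, obtain vital status where consent allows.
- Report with the OS estimate how many patients were censored at or after progression without further survival follow-up.

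The cost is a wording amendment and occasional phone or email contacts that the protocol already foresees. Treatment does not change, and follow-up is still in force in this version.

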# 3.6.3 Lost to Follow-Up

A participant will be considered lost to follow-up if he or she fails to return for three (3) consecutive scheduled visits and is unable to be contacted by the study site staff.

The following actions must be taken if a participant fails to return to the clinic for a required study visit:

- The site will attempt to contact the participant and reschedule the missed visit within five (5) business days and counsel the participant on the importance of maintaining the assigned visit schedule and ascertain if the participant wishes to and/or should continue in the study.
- Before a participant is deemed lost to follow-up, the investigator or designee will make every effort to regain contact with the participant (where possible, 3 telephone calls and, if necessary, an IRB approved certified letter to the participant's last known mailing address or local equivalent methods). These contact attempts should be documented in the participant's medical record or study file.
- Should the participant continue to be unreachable, he or she will be considered to have withdrawn from the study with a primary reason of lost to follow-up.

## 4 CONCOMITANT MEDICATIONS/MEASURES AND CONSIDERATIONS

## 4.1 TUMOR LYSIS SYNDROME

- 4.1.1 Hydration and Fluid Monitoring Guidelines
  - a. Oral hydration: All subjects must be well hydrated (i.e., volume replete). Begin oral hydration equal to approximately 30 mL/kg/day (~6–8 cups of liquid per day), starting 48 hours prior to the planned first dose of carfilzomib.
  - b. IV hydration: Adequate hydration is required prior to dosing in Cycle 1, especially for patients at high risk of tumor lysis syndrome or renal toxicity. The recommended hydration includes both oral fluids (30 ml per kg at least 48 hours before Cycle 1, Day 1) and intravenous fluids (250 ml to 500 ml of appropriate intravenous fluid prior to each dose in Cycle 1). If needed, given an additional 250 to 500ml following carfilzomib administration. Continue oral and/or intravenous hydration, as needed, in subsequent cycles. Monitor patients for evidence of volume overload and adjust hydration to

Version Date: 01/01/2024

individual patient needs, especially in patients with or at risk for cardiac failure. Total volume will be determined at the discretion of clinician and volume status of patient.

c. In subjects considered to be still at risk for TLS at completion of Cycle 1, hydration should be continued into subsequent cycles if clinically indicated.

# 4.1.2 Laboratory Monitoring

- a. Appropriate chemistries, including creatinine, and complete blood counts (CBC) with platelet count should be obtained and reviewed prior to carfilzomib dosing. Results of laboratory studies must be reviewed and deemed acceptable prior to administering the carfilzomib dose.
- b. Subjects with laboratory abnormalities consistent with lysis of tumor cells (e.g., serum creatinine ≥ 50% increase, LDH ≥ 2-fold increase, uric acid ≥ 50% increase, phosphate ≥ 50% increase, potassium ≥ 30% increase, calcium ≥ 20% decrease) prior to dosing should not receive the scheduled dose

## 4.1.3 Clinical Monitoring

- a. Signs and symptoms indicative of TLS, such as fevers, chills/rigors, dyspnea, nausea, vomiting, muscle tetany, weakness, or cramping, seizures, and decreased urine output.
- b. Patients will be admitted to the inpatient hospital and observed while receiving Cycle 1 Days 1 and 2 of therapy.

# 4.1.4 Management

- a. If TLS occurs, cardiac rhythm, fluid, and serial laboratory monitoring should be instituted. Correct electrolyte abnormalities, monitor renal function and fluid balance, and administer therapeutic and supportive care, including dialysis, as clinically indicated.
- b. All cases of TLS must be reported to Amgen as a Serious Adverse Event (SAE) through the normal process within 24 hours of the clinical site becoming aware of the event.

# 4.1.5 Optional medication for high risk TLS patients:

a. Allopurinol is optional and will be prescribed at the Investigator's discretion. These subjects may receive allopurinol 300 mg PO BID (Cycle 1 Day -2, Day -1), continuing for 2 days after Cycle 1 Day 1 (total of 4 days), then reduce dose to 300 mg PO QD, continuing through Day 17 of Cycle 1. Allopurinol dose should be adjusted according to the package insert. Subjects who do not tolerate allopurinol should be discussed with the Lead Principal Investigator.

## 4.2 TRANSFUSIONS/GROWTH FACTORS

Subjects may receive RBC or platelet transfusions if clinically indicated.

Colony-stimulating factors may be used if neutropenia occurs but should not be given prophylactically.

## 4.3 ANTI-COAGULATION

Oral Aspirin 81 mg or 325 mg or suitable alternative anti-coagulation for thrombotic prophylaxis every day for the duration of their participation in the study. Anti-Xa levels will need to be followed in those patients with eGFR < 30 ml/min and receiving enoxaparin. In general,

Version Date: 01/01/2024

temporarily holding of prophylactic or treatment doses (for venous thrombo-embolism) anticoagulation with either aspirin or enoxaparin peri-procedurally (e.g., for bone marrow biopsies) is not required. However, in rare cases, the clinician may hold when clinically indicated.

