# 3.6.1 Criteria for removal from protocol therapy

- Patients with medically concerning grade 3 or 4 adverse events related to drug therapy may be taken off therapy at the discretion of the principal investigator.
- Patients require more than 2 dose reductions of carfilzomib.
- Toxicity has not resolved after 2 weeks of withholding treatment or up to 3 weeks for infection related treatment
- Grade 3 non-blistering rash or blistering rash of any grade
- Grade 3 neuropathy
- Grade 3 hypersensitivity reaction
- Diagnosis of posterior reversible encephalopathy (PRES) or thrombotic microangiopathy (TMA)
- Patient completes the protocol (as outlined in Section 3.2)
- Progression of disease
- Patient chooses to go off therapy
- The principal investigator may remove patient from protocol therapy if deemed necessary due to medical conditions, compliance, etc.
- Patient becomes pregnant.

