### 4.4 HSV AND VSV PROPHYLAXIS

Oral Valacyclovir of 500 mg daily or oral Acyclovir of 800 mg BID throughout all cycles in which carfilzomib is given.

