# Contraception

Females of childbearing potential (FCBP) enrolled in this protocol must agree to use two reliable forms of contraception simultaneously or to practice complete abstinence from heterosexual intercourse during the following time periods related to this study: 1) for at least 28 days before starting lenalidomide; 2) throughout the entire duration of lenalidomide treatment; 3) during dose interruptions; and 4) for at least 28 days after lenalidomide discontinuation.

The two methods of reliable contraception must include one highly effective method and one additional effective (barrier) method. FCBP must be referred to a qualified provider of contraceptive methods if needed. The following are examples of highly effective and additional effective methods of contraception:

- o Highly effective methods:
  - Intrauterine device (IUD)
  - Hormonal (birth control pills, injections, implants)
  - Tubal ligation
  - Partner's vasectomy
- o Additional effective methods:
  - Male condom
  - Diaphragm
  - Cervical Cap

Because of the increased risk of venous thromboembolism in patients with multiple myeloma taking lenalidomide and dexamethasone, combined oral contraceptive pills are not recommended. If a patient is currently using combined oral contraception the patient should switch to one of the effective method listed above. The risk of venous thromboembolism continues for 4–6 weeks after discontinuing combined oral contraception. The efficacy of contraceptive steroids may be reduced during co-treatment with dexamethasone.

Version Date: 01/01/2024

Implants and levonorgestrel-releasing intrauterine systems are associated with an increased risk of infection at the time of insertion and irregular vaginal bleeding. Prophylactic antibiotics should be considered particularly in patients with neutropenia.

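### Section 4.3 ties daily thromboprophylaxis to study participation, so as worded it runs into follow-up off both carfilzomib and lenalidomide, although the treatment period was probably meant

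*Combined protocol and SAP*

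**What the plan says.** Section 4.3 sets aspirin 81 mg or 325 mg, or a suitable alternative, as thrombotic prophylaxis "every day for the duration of their participation in the study". It adds that holding around procedures is generally not needed, though a clinician may hold in rare cases.

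The protocol separates leaving therapy from leaving the study. Section 3.6.1 lists "Patient completes the protocol (as outlined in Section 3.2") among the reasons to come off therapy. Section 3.6.2 has its own list for coming off study, and completing treatment is not on it.

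After treatment, the patient stays on study in several ways:

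- Section 3.1.2: after two years of maintenance, "patients will be followed by clinical and laboratory examination every 3-6 months until disease progression requiring treatment".
- Study Calendar (3.4), footnote j: "Patients who are taken off treatment will continue to be followed for survival by phone or clinic visit".
- Section 3.6.2: patients on non-protocol therapy for symptomatic myeloma "may remain on study for evaluation (by phone, email, or clinic visit) of survival per study schedule", at the investigator's discretion.
- Section 3.6.2: patients without progression who "choose to continue lenalidomide maintenance beyond 32 cycles at an outside facility may stay on study", also at the investigator's discretion.

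**The concern.** A prophylactic drug is normally given for as long as the risk it guards against. Here the stated risk is drug-related, but the stated duration is study participation. Read literally, a patient who stopped early for toxicity, or who finished cycle 32 and is now only observed, must still take a daily antithrombotic drug for as long as follow-up lasts.

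What is at stake is possible bleeding without a stated benefit. That is a clinical inference, and the documents put no number on it. Two features add to it. Under 6.1, beyond 30 days after the last intervention only serious and related events need to be recorded, so a non-serious bleed on prophylaxis in follow-up would not have to be captured. Under 8.8, any non-compliance with the protocol is a deviation, so a clinician who sensibly stopped aspirin after treatment would, on the literal text, be departing from it.

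**Working it through.** The plan gives no figure to reproduce. The check is a comparison of periods and wording.

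**1. When protocol drug ends.** Induction is 8 cycles (3.1.1), extended dosing phase I is 12 (3.2.4) and optional phase II is 12 (3.2.5). Cycles last 28 days.

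- Carfilzomib: cycles 1 to 8, so 8 × 28 = 224 days.
- Lenalidomide without phase II: 8 + 12 = 20 cycles, so 20 × 28 = 560 days.
- Lenalidomide with phase II: 20 + 12 = 32 cycles, so 32 × 28 = 896 days.

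These are scheduled lengths and exclude delays, such as the wait of up to 5 weeks for stem cell harvest.

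**2. When participation ends.** Follow-up under 3.1.2 runs to progression that needs treatment. Survival follow-up under footnote j, and continued stay under 3.6.2, have no calendar limit. The rule in 4.3 therefore has no fixed end either.

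**3. How comparable rules are worded.**

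| Measure | Place | Duration |
|---|---|---|
| Antiviral prophylaxis | 4.4 | "throughout all cycles in which carfilzomib is given" |
| Contraception, women of childbearing potential | Appendix B | 28 days before, "throughout the entire duration of lenalidomide treatment", during dose interruptions, and 28 days after |
| Thromboprophylaxis | 4.3 | Study participation, no link to drug |

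**4. Where the documents place the thrombotic risk.** Section 14.2.2 describes venous thromboembolism in patients treated with lenalidomide combinations. Section 8.5.2.1 associates venous thrombosis with carfilzomib. Appendix B refers to lenalidomide with dexamethasone. The extended-dosing table in 3.3.6 lists venous thrombosis/embolism among common lenalidomide toxicities. No section gives a reason for prophylaxis in a patient off both drugs.

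**5. Whether any stop or hold reaches follow-up.** Sections 3.3.2.3 and 3.3.5.2 hold prophylaxis at platelets below 25 × 10^9/L, but both are written for events during a cycle. The hold in 4.3 is for rare cases and follows a sentence about procedures. Neither is a stop at the end of treatment.

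**6. Who falls under the literal rule in follow-up.**

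- Off both drugs, whether after cycle 32 or after stopping early: covered, with no stated reason.
- On study while taking lenalidomide at an outside facility: covered, and with a drug-based reason.
- On non-protocol therapy and kept on study for survival: covered on the words alone, although contact may be only by phone or email.

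The gap concerns the first group. The third is a strained extension of the text and carries little weight.

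**The case against.** The strongest reply is that this is loose phrasing. Section 3.2.2.2 uses almost the same participation wording for the free supply of lenalidomide, whose protocol dosing ends by cycle 32. Section 4 is headed as concomitant medications, the platelet holds assume cycles, and the long-term follow-up data list in 6.1.1 does not include prophylaxis use. Together these suggest that the authors meant the treatment period.

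That stands as evidence of intent, and it limits the size of the point. It does not settle the text. Section 3.2.2.2 describes the supply of a drug whose schedule is fixed elsewhere, so loose wording there does little harm. Section 4.3 is the only place that sets how long prophylaxis lasts.

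It is also fair to say that the present wording protects one group: on-study patients who continue lenalidomide outside. Any correction should keep that protection. A simple phrase such as while receiving drug would also be unclear for days 22 to 28, dose interruptions and the harvest delay.

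A further reply is that all participants had completed the maintenance phase by February 6, 2023 (Study Calendar, footnote g), so little is left to govern. That holds for protocol dosing. It does not hold for follow-up, which is where the wording now applies.

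**Conclusion.** The point holds as a minor safety wording correction. As written, 4.3 requires daily prophylaxis through open-ended follow-up off both drugs, and the documents give no reason for it there. The probable intent was the treatment period.

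A reader might go further and infer that the sponsor deliberately chose indefinite prophylaxis, that patients took it in follow-up because of 4.3, or that bleeding harm resulted. The documents support none of these. The neighbouring text points away from such an intent, no section reports prophylaxis use in follow-up, and no bleeding rate is given. Nor does every follow-up patient lack a reason for prophylaxis, since some may still take lenalidomide outside.

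No endpoint, sample size or analysis changes. The conclusion rests on reading participation in the sense used in 3.6, where leaving therapy and leaving the study are different events.

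**What to change.** Replace the duration phrase in 4.3 with:

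> every day from cycle 1 day 1 through the end of the last cycle of protocol carfilzomib or lenalidomide, including planned off-drug days and dose interruptions, except when held under 3.3.2.3 or 3.3.5.2, and for as long as an on-study patient continues lenalidomide at an outside facility; prophylaxis under this protocol is not required once the patient is off both drugs, when any further use is decided by the treating physician.

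Therapeutic anticoagulation for a thrombotic event is unaffected. The sponsor may add a brief washout, or instead state a reason for continuing off drug if one exists.

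The cost is one short amendment, with no data or analysis work. If treatment was always meant, the change alters nothing intended. Its practical use now is to tell clinicians what applies to patients in follow-up.
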